9.1.3. Double-Blind Treatment Phase

Day 1/Day of Randomization

If the subject meets all of the inclusion and none of the exclusion criteria, he or she is eligible to be randomly assigned to receive rivaroxaban or placebo at the Day 1 visit.

Randomization should occur on the day the subject leaves the hospital; randomization will also be permitted the day after the subject leaves the hospital. Randomization may occur at the hospital, clinic or other discharge destination.

At the randomization visit, before randomization occurs, site staff must review the visit schedule and the importance of completing the study with both the subject and any family members present. Randomization should not occur if the subject:

- does not have transportation to study visits
- does not believe they will have sufficient support to comply with the protocol
- is being discharged to a destination other than home and acceptability of study participation has not been confirmed with the accepting physician
- post-discharge anticoagulation or thromboprophylaxis is planned

Also, before randomization occurs, site staff should review eligibility criteria, including concomitant medications administered during the index hospitalization and planned at discharge. Particular attention should be paid to ensure that acceptable types and doses of thromboprophylaxis were used during the index hospitalization, and that prohibited medications were not administered and are not planned.

After randomization, the first dose of study drug should be administered as soon as possible and no later than the day after the subject leaves the hospital. The time of the first dose should be recorded as accurately as possible. The first dose also should not be delayed to allow administration under supervision. The first dose does not need to be delayed because of the recent administration of LMWH or UFH. The administration date and time of the first dose of study drug will be recorded in the source document and eCRF. The subject will be instructed to take study drug daily through Day 45. **Regardless of the day on which the Day 45 Visit occurs, no study drug may be taken after Day 45.**

Also, at the randomization visit, the importance of reporting signs and symptoms associated with bleeding, DVT and PE will be stressed. Subjects and family members, as appropriate, will be counseled and given educational material on the signs and symptoms associated with DVT, PE and bleeding.

For bleeding events, subjects and family members as appropriate, will be instructed:

- To seek medical attention if they develop bleeding
- To contact the investigative site staff or study investigator before the next dose of study medication is due
- To inform treating health care providers about study participation

Subjects and family members, as appropriate will also be instructed:

- About the subject's risk of DVT and PE
- About the signs and symptoms of DVT and PE
- To seek medical attention if they develop any of these signs or symptoms
- To contact the investigative site staff or study investigator as soon as symptoms develop and before the next dose of study medication is due
- To inform treating health care providers about study participation and their risk of DVT and PE.

The subject's family should be instructed to have a low threshold to contact the site and if necessary an unscheduled visit can be performed.

Treatment Visits

Subjects will be instructed to adhere to the visit schedule in the TIME AND EVENTS SCHEDULE. Treatment visits should be conducted at the site, but to allow for as complete follow up as possible, they may be conducted at home or at another discharge destination, if allowed by local regulatory and IRB/Ethics Committee requirements. Day 7 and Day 75 visits may be conducted as a telephone visit. Visits conducted at home may only be performed by medically qualified personnel (eg, training and education) as delegated by the Principal Investigator and as documented in the Delegation Log. If a visit in the subject's presence cannot be achieved, telephone contact with the subject should be attempted. If telephone contact with the subject cannot be achieved, the site should attempt to contact others who have knowledge of the subject as allowed by local and IRB/Ethics Committee requirements.

Day 7 Visit

The Day 7 Visit may be conducted at the clinic or other discharge destination including a home visit if allowed by local requirements or as a telephone visit. Visits conducted at home may only be performed by medically qualified personnel as delegated by the Principal Investigator and as documented in the Delegation Log. If the information is obtained via telephone contact, written documentation of the communication must be available for review in the source documents. The visit window is -2 days/+5 days. Study personnel will confirm sufficient drug supply to allow for daily dosing through the Day 21 Visit, and will reinforce the dosing schedule and procedure to follow if a dose is missed. The clinical status review for suspected outcome events will be completed, as will the symptom assessment, consisting of a set of scripted questions

(Attachment 4). Adverse events will be collected as specified in Section 12, and concomitant medication will be collected as specified in Section 8.

Subject counseling provided at the randomization visit will be repeated in detail.

Day 21 Visit

The Day 21 Visit may be conducted at the clinic or other discharge destination including a home visit if allowed by local requirements. Visits conducted at home may only be performed by medically qualified personnel (eg, training and education) as delegated by the Principal Investigator and as documented in the Delegation Log. The Day 21 Visit should not be conducted as a telephone visit. Attendance in person is required to allow study drug dispensing. The visit window is -3 days/+7 days to ensure compliance. Study drug accountability will be performed and a supply of 30 tablets dispensed. Site staff will reinforce the dosing schedule and procedure to follow if a dose is missed. The clinical status review for suspected outcome events will be completed, as will the symptom assessment, consisting of a set of scripted questions (Attachment 4) and a clinical assessment. Adverse events will be collected as specified in Section 12, and concomitant medication will be collected as specified in Section 8.

Subject counseling provided at the randomization and Day 7 Visits will be again repeated in detail.

Day 45 Visit

The Day 45 Visit may be conducted at the clinic or other discharge destination including a home visit if allowed by local requirements. Visits conducted at home may only be performed by medically qualified personnel (eg, training and education) as delegated by the Principal Investigator and as documented in the Delegation Log. The Day 45 Visit should not be conducted as a telephone visit. The visit window is -0 days/+4 days to ensure all events through the end of treatment are captured. The last dose of study drug will be administered on Day 45 regardless of the day of the Day 45 visit. **Regardless of the day on which the Day 45 Visit occurs, no study drug may be taken after Day 45.** Study drug accountability will be performed. The clinical status review for suspected outcome events will be completed, as will the symptom assessment, consisting of a set of scripted questions (Attachment 4) and a clinical assessment. Adverse events will be collected as specified in Section 12, and concomitant medication will be collected as specified in Section 8.

Subject counseling provided at the randomization, Day 7, and Day 21 Visits will be again repeated in detail.

Unscheduled Visit

Subjects may be seen by the investigator between scheduled visits for any reason such as:

- Suspected efficacy or bleeding outcome event
- Early study drug permanent discontinuation
- Adverse event, based upon the severity and clinical judgment of the investigator
- Lost medication requiring replacement

Early Study Drug Permanent Discontinuation/Early Withdrawal from Study

If the subject permanently discontinues study drug before Day 45, he/she should be instructed to complete an unscheduled visit and the remaining scheduled visits, including the Day 7 (-2d/+5 d) and Day 21 (-3d/+7d) visits and the Day 45 (+4d) and Day 75 ($\pm 5d$) visits (see [TIME AND EVENTS SCHEDULE](#)). Because the primary efficacy analysis of the study is based upon the intention-to-treat (ITT) principle, the investigator should inform the subject of the importance of returning for all study visits. It is imperative for the integrity of the trial and results to have vital status and other outcomes ascertainment. If the subject is unwilling or unable to return for any visits, the site should collect as much follow-up information as possible, including contacting the subject or legally acceptable representative by telephone or by mail to determine vital status and if an outcome has occurred, as agreed to by the subject during the initial informed consent process. If applicable, vital status and other outcomes should be obtained by reviewing the subject's medical or public records unless this contact is not allowed by local regulations.

If the subject withdraws consent from the study, this must be documented in the source document and the subject will be asked to supplement the withdrawal of consent with a signed written statement documenting refusal for all subsequent contact.

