10. SUBJECT COMPLETION/WITHDRAWAL

10.1. Completion

The total duration for a subject who completes the study after randomization is expected to be 75 days.

All feasible efforts and measures will be made to collect complete vital status and other outcome data from randomization to the Day 75 ($\pm 5d$) visit for each subject randomized in this study, regardless of compliance with study drug or visits. For subjects who are lost to follow-up or withdraw consent from the study, efforts will be made to obtain their vital status and other outcomes from permitted sources.

It is important to note that withdrawal of consent does not withdraw permission to collect vital status and other outcomes. Withdrawal of permission to collect vital status and other outcomes must be made separately. In cases where subjects indicate they do not want to “continue”, investigators must determine whether this refers to discontinuation of study treatment (the most common expected scenario), unwillingness to attend follow-up visits, unwillingness to have telephone contact, unwillingness to have any contact with study personnel, or unwillingness to allow contact with a third party (eg, family member, doctor). In all cases, every effort must be made to continue to follow the subject, and vital status and other outcomes must be determined for all randomized subjects.

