10.3. Withdrawal From the Study

A subject will be withdrawn from the study for any of the following reasons:

- Lost to follow-up (only after all means of all subsequent contact, including locator services where permitted by law, up until the Day 75 ($\pm 5d$) visit, have been exhausted, lost to follow-up will be declared).
- Withdrawal of consent (unless specifically refused by the subject, subject contact will be made to obtain vital status and other outcomes at the Day 75 ($\pm 5d$) visit).

If a subject is lost to follow-up, every reasonable effort must be made by the study site personnel to contact the subject and determine the reason for discontinuation/withdrawal. The measures taken to follow up must be documented.

Study drug assigned to the withdrawn subject may not be assigned to another subject. Subjects who withdraw will not be replaced.

If a subject withdraws consent from study or is lost to follow-up, his or her vital status and other outcomes will be collected at the Day 75 ($\pm 5d$) visit either by telephone or in person, or if applicable, by a review of the subject's medical or public records unless this contact is not allowed by local regulations.

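### Protocol 9.1.3 asks every subject who withdraws consent to sign a refusal of all further contact, at odds with the rules in 10.1 and 10.3 that keep outcome collection going after withdrawal

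*Protocol*

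**What the plan says.** Protocol 9.1.3, in its text on early study drug discontinuation and early withdrawal, deals with withdrawal of consent in one sentence. The withdrawal is documented in the source record and "the subject will be asked to supplement the withdrawal of consent with a signed written statement documenting refusal for all subsequent contact". The request is made of every subject who withdraws consent.

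Protocol 10.1 states that "withdrawal of consent does not withdraw permission to collect vital status and other outcomes". It adds: "Withdrawal of permission to collect vital status and other outcomes must be made separately". It then lists what a subject who does not want to go on may mean (stopping study drug, no visits, no telephone contact, no contact with study staff, no third-party contact) and requires the investigator to find out which applies. Whatever the answer, "every effort must be made to continue to follow the subject, and vital status and other outcomes must be determined for all randomized subjects".

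Protocol 10.3 provides, for a subject who has withdrawn, that "unless specifically refused by the subject, subject contact will be made to obtain vital status and other outcomes"; the time set for this is Day 75. Outcomes are then collected by a call or a visit, and otherwise "by a review of the subject's medical or public records unless this contact is not allowed by local regulations". SAP 1.2 repeats that outcomes are collected at Day 75 after withdrawal of consent.

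SAP 2.1 defines the last outcome-evaluation date by the last clinic or telephone visit at which outcome status was ascertained. SAP 2.3 censors event-free subjects at Day 45 or that date, whichever is earlier.

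**The concern.** Sections 10.1 and 10.3 start from continued follow-up and narrow it only as far as the subject asks. The 9.1.3 sentence starts from the other end: the only document put before a withdrawing subject is the most complete refusal of contact. A subject who withdraws consent but would have accepted one telephone call may sign it, and the 10.3 exception then applies.

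The primary analysis is intention-to-treat over 45 days. Section 9.1.3 itself, a paragraph earlier, treats complete outcome ascertainment as essential to the integrity of the trial. SAP 5.2.2 expects missing follow-up not to affect the conclusion and relies on extensive collection efforts, which this sentence works against. If withdrawal is related to both prognosis and treatment, censoring at the last contact could bias the hazard ratio, and enrolling more subjects would not repair that.

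**Working it through.** **Step 1. The texts side by side.**

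| Question | Protocol 9.1.3 | Protocol 10.1, 10.3; SAP 1.2 |
|---|---|---|
| What follows withdrawal of consent? | A request to sign a refusal of all later contact | Outcomes are still collected; contact is the default (10.3) |
| Is the level of refusal established first? | Not mentioned | Required (10.1) |
| How does outcome collection end? | Not addressed; the form covers contact only | By a separate withdrawal of permission (10.1) |

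The conflict concerns contact. The 9.1.3 form does not refuse record review.

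**Step 2. From contact to censoring.** A withdrawn subject reached by telephone at Day 75 has a last outcome-evaluation date after Day 45 and, if event-free, is censored at Day 45. A subject who has signed has no later clinic or telephone visit and, if event-free, is censored at the last visit before withdrawal. As SAP 2.1 is worded, a clean record review does not move that date. If it falls before Day 45, SAP 4.2 counts such a subject as a non-completer of the study.

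**Step 3. The plan's own figures.** Inputs from Protocol 11.2: HR 0.60, two-sided alpha 0.05, power 90%, placebo rate 2.5%, 1:1 allocation.

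- Events (Schoenfeld): D = 4(1.960 + 1.282)² / (ln 0.60)² = 161.07. The plan states 161.
- Subjects: pooled rate = 0.025 × (1 + 0.60)/2 = 0.020; N = 161/0.020 = 8,050. The plan states about 8,000. There is no inflation for lost follow-up.
- Expected events at 8,000 subjects: 8,000 × 0.020 = 160.

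**Step 4. Size of the loss.** The documents give no withdrawal rate, so a range is assumed. Let w be the fraction withdrawing and f the share of the 45-day risk lost (0.5 to 1). Withdrawers are taken to be at average risk, with nothing recovered from records.

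- Events lost = 160 × w × f
- Power = Φ(√D × |ln 0.60|/2 − 1.960), where D is the number of events remaining; with 160 events it is 0.898
- Subjects needed for 161 events = 161 / [0.020 × (1 − w × f)]

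| w | Events lost | Power | Subjects for 161 events |
|---|---|---|---|
| 1% | 0.8 to 1.6 | 0.897 to 0.895 | 8,090 to 8,131 |
| 2% | 1.6 to 3.2 | 0.895 to 0.892 | 8,131 to 8,214 |
| 5% | 4 to 8 | 0.891 to 0.883 | 8,256 to 8,474 |
| 10% | 8 to 16 | 0.883 to 0.865 | 8,474 to 8,944 |

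These are the losses if every withdrawer becomes uncontactable. The share due to the 9.1.3 sentence is smaller: only those who would otherwise have accepted contact.

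Amendment INT-7 raised the ceiling to about 12,000 because the pooled event rate was low. If 161 events came from 12,000 subjects, the rate would be 161/12,000 = 1.34%, and 1% of subjects would carry 120 × 0.0134 = 1.6 events, the same upper figure. Further enrolment can replace lost events only below that ceiling. SAP Table 1 already needs 13,400 subjects at a 1.5% placebo rate.

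**The case against.** The strongest reply is that the sections can be read in sequence. The investigator first carries out the 10.1 enquiry, and the signed statement then records a refusal that the subject has already made, as the separate act that 10.1 calls for. The text permits this reading, so a claim that the two rules cannot both be followed would go too far. But 9.1.3 does not say it, and a site reading that section alone would put the form to every withdrawer.

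Several stronger readings are tempting and not supported:

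- *That a subject who only wants to stop tablets or visits is turned into a total refuser.* The preceding paragraph of 9.1.3 covers those subjects and keeps them in follow-up by visit, telephone, mail or records. The signed statement is triggered only by withdrawal of consent.
- *That everyone who signs is irrecoverably lost.* Signing is requested, not required. Sections 10.1 and 10.3 and SAP 1.2 keep permitted sources or record review open, and no rule excludes an adjudicated event by Day 45 found that way. Nothing says a refusal is irreversible.
- *That the SAP's only answer is a count of events needed to overturn the result.* SAP 5.2.2 also summarises subjects and time with missing follow-up, and SAP 4.2 reports non-completers with reasons by arm. These show the loss; they do not prevent it.
- *That a Day 75 contact comes too late.* It looks back over the primary window, since the Attachment 4 questions cover the time since the last contact.

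It is also fair to say that nothing in the documents shows withdrawal to be related to treatment. Bleeding leads to interruption or discontinuation of study drug with follow-up continuing. That withdrawal might be informative is an inference.

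**Conclusion.** The inconsistency is real and stands in the current text. Section 9.1.3 solicits, without condition, a refusal that 10.1 and 10.3 treat as a specific and separate choice. Because the SAP ties event-free follow-up to clinic or telephone visits, this can avoidably censor some withdrawn subjects before Day 45.

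The size is modest: about 0.8 to 1.6 primary events per 1% of 8,000 subjects withdrawing, with power moving from 0.898 to 0.895–0.897. This assumes average risk, half to all of the 45 days lost and no recovery from records. At 10% withdrawing, 8 to 16 unobserved events could matter to the planned analysis of how many extra events would overturn superiority. The reason to act is possible informative censoring, which the documents neither establish nor exclude, and not loss of power. A reader should not infer that the primary result is compromised or that the sample size needs to change.

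**What to change.** Amend the 9.1.3 sentence so that the site:

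1. first records the level of withdrawal using the options in 10.1;
2. requests a signed refusal of all contact only from a subject who specifically states that refusal;
3. documents any refusal of outcome collection or record review separately.

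Sections 9.1.3, 10.1 and 10.3 and SAP 1.2 would then describe one procedure. The cost is protocol and site-instruction wording, with no change to the sample size or the analysis.

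A telephone or record check at Day 45 (+4 days) for withdrawn subjects who have not refused is optional. It would shorten recall and give a second chance of contact, but the Day 75 contact already covers the window.

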9.1.4. Post-treatment Phase (Follow-Up)

Day 75 Visit

The Day 75 Visit may be conducted at the clinic or other discharge destination including a home visit if allowed by local and IRB/Ethics Committee requirements or by a telephone visit. Visits conducted at home may only be performed by medically qualified personnel (eg, training and education) as delegated by the Principal Investigator and as documented in the Delegation Log. The visit window is -5 days/+5 days. The clinical status review for suspected outcome events will be completed, as will the symptom assessment, consisting of a set of scripted questions ([Attachment 4](#)). Adverse events will be collected as specified in Section 12, and concomitant medication will be collected as specified in Section 8.

If the information is obtained via telephone contact, written documentation of the communication must be available for review in the source documents.

Randomization in this study is preceded by a hospitalization for an acute illness and the study drug treatment phase extends for 45 days after randomization to correspond to the period of greatest risk for VTE. Chronic therapy with the study drug is not being tested. For these reasons, rivaroxaban will not be provided to the subject after the subject completes the Day 75 (± 5 d) visit unless required by local regulations. It will only be after data from the entire study is analyzed that the sponsor will determine if the population at risk will benefit from treatment.

9.2. Efficacy Evaluations and Outcomes

As described in Section 1.1.5, PE is reported by physicians to be the most commonly missed or delayed diagnosis. As MARINER is a symptomatic event-driven trial it is critical all efficacy outcome events, including symptomatic PE are appropriately diagnosed. Any suspected event that includes symptoms or signs suggestive of a PE must be sent for adjudication. Investigators are encouraged to give careful consideration of the diagnosis of PE for subjects admitted under their care with symptoms of or exacerbations of conditions such as (pneumonia, bronchitis, heart failure, cardiorespiratory failure and exacerbation of COPD). Investigators are also strongly encouraged to expeditiously contact the treating physician for any subject hospitalized with any of these conditions.^{2,32,12}

9.2.1. Efficacy Evaluations, Outcomes and Adjudication

This is a clinical outcomes study. The primary efficacy outcome is the composite of all symptomatic VTE events (lower extremity DVT and non-fatal PE) and VTE-related death (death due to PE or death in which PE cannot be ruled out as the cause).

Secondary efficacy outcomes are:

- VTE-related death (death due to PE or death in which PE cannot be ruled out as the cause)
- Symptomatic VTE (lower extremity DVT and non-fatal PE)
- The composite of symptomatic VTE (lower extremity DVT and non-fatal PE) and ACM
- The composite of symptomatic VTE (lower extremity DVT and non-fatal PE), MI, non-hemorrhagic stroke and CV death (death due to a known CV cause and death in which a CV cause cannot be ruled out; by this definition, a VTE-related death is considered a CV death)
- ACM

Exploratory efficacy outcomes are:

- Symptomatic lower extremity DVT
- Symptomatic non-fatal PE
- Symptomatic upper extremity DVT
- MI
- Non-hemorrhagic stroke

- Re-hospitalization for symptomatic VTE (lower extremity DVT and non-fatal PE) within 30 days after randomization

Submission of a suspected event for adjudication will be required for:

- All deaths
- Suspected events that include symptoms or signs suggestive of PE or DVT.
- Performance of any imaging or other diagnostic study that could yield an incidental diagnosis of PE or DVT.
- Suspected events that include acute coronary syndrome or MI. Chest pain determined not to be cardiac in origin does not need to be sent for adjudication.
- Suspected events that include symptoms compatible with a TIA or stroke. Events determined not to be a TIA or stroke (eg, seizure, hypoglycemia) do not need to be sent for adjudication.

Any clinical event that suggests the possibility that an efficacy outcome event has occurred (including ACS and TIA) should be indicated on the Clinical Status page of the eCRF and will be sent for adjudication. Examples of objective testing diagnostic procedures that may have been performed as part of the standard of care are listed in [Attachment 2](#). For imaging studies, a copy of the original study should be sent with the adjudication package. For other tests, a report of the results will suffice. All clinical data must be sent to CEC for adjudication. The CEC may request additional imaging in order to ensure appropriate adjudication. The CEC will apply the definitions (see [Attachment 1](#)) contained in the CEC charter to adjudicate and classify the events while blinded to treatment assignment. Adjudicated results will be used for final analyses.

